- The main technology enabler in this intervention, was the digitalization in 2018 of the home visit assessment tool in the Electronic Patient Records (EPR) for the boroughs. In addition, a way of registering falls in the same EPR as well as a clear routine for how to document the multifactorial assessment and the follow up within this system, was a great support for those who did the home assessments and follow-up interventions. Digitalization of the fall reports in 2018 from the Injury Clinic, also was an improvement.

Timeline

Improving care coordination is a process. The investigators have, however, chosen to define these dates as the start of intervention, as this was the time when the systematic needs assessment together with the interdisciplinary and cross-sectoral approach to the fall-risk-prevention-problem, started.

These were the milestones which were chosen as start dates of the intervention:

1. Start of intervention in Nordstrand borough is set to January 1, 2015.

The Chief Medical Officer in Nordstrand mobilized the health professionals in a systematic needs assessment. They improved case finding, developed a checklist for multifactorial falls risk assessment through home visits, recruited more elderly at risk into exercise programs, and started education of health professionals including the GPs in coordination with the geriatricians at the University Hospital and local nursing homes. They also improved primary prevention with winter road safety measures and education of the general elderly population on fall risks and safety measures.

After Østensjø and the Injury Clinic at Oslo University Hospital joined the intervention in September 2016, the intervention in Nordstrand was done in collaboration and coordinated with these partners.

2. Start of intervention in Østensjø borough is set to September 1, 2016.

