Østensjø started a collaboration with Nordstrand borough and the Injury Clinic in September 2016 after a grant proposal ("Samhandlingsmidler") was awarded funding. This led to a development of a formal multifactorial falls and fracture risk assessment tool for GPs, a revision of the interdisciplinary falls risk assessment tool from Nordstrand for home visits, establishing referral pathways within primary care and with specialist care established. In addition, education programs for both GPs and other health professionals in primary care was strengthened. Local champions were chosen and interdisciplinary working groups were established.

3. The Injury Clinic supported case finding from September 2017

All municipalities started receiving **fall reports** regarding consenting patients with fall injuries treated at the Injury Clinic at the University Hospital in Oslo from September 2017. This improved the case finding in both Nordstrand and Østensjø, who already had a coordinated care plan in place, which were presumed to be the crucial part of the intervention. The 13 other municipalities did not have the same coordinated care. Their patients received care as usual, which varied between the boroughs.

4. The end of the study period is set to December 31. 2019

The intervention in Oslo expanded to include most of the city boroughs after 2019. From January 2020 five more boroughs started care coordination, another five during 2021 and further one in 2022. The end of the study period with comparison between the two boroughs who started this intervention and the others, is therefore set to the end of 2019, before the 13 others began their systematic coordination of care.

Statistical Analysis Plan

The investigators will use a controlled before and after study design to evaluate this intervention.

The cohort

All elderly 65 age or older in Oslo are included in Oslo Fall Cohort with registry data from Statistics Norway, the National Population Registry, Norwegian Patient Registry (NPR), and the Electronic Patient Records for the health services in the local municipalities. Data is available on all participants from 2010 and the investigators will start following them from January 2012 until December 2019 with the intervention starting as specified in the timeline (see above). The study will follow each cohort participants prospectively and analyze the data by Cox proportional hazards regression or similar.

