Fall injury will be included as a time-varying exposure variable. The individuals in the cohort are all registered as non-fallers until they are registered with a new fall injury in the NPR database, when they shift status to fallers.

Exposure categories

• Fallers in the intervention boroughs

Fallers 65+ years from the borough of Nordstrand from January 1. 2015 Fallers 65+ years from the borough of Østensjø from September 1. 2016

• Fallers in the control boroughs

Fallers 65+ years from all the 13 other boroughs of Oslo.

Non-fallers

All non-fallers from the complete Oslo population 65+ years.

Main analysis: In the main analysis (2015-2019), fallers from the two intervention boroughs, Nordstrand (from January 2015) and Østensjø (from September 2016), will be compared with fallers from the control boroughs during the intervention. In addition, the two categories of fallers will also be compared with the non-fallers. A similar analysis will be performed before the intervention started using data from 2012-2013. Any differences between the intervention and control boroughs before the intervention started will be taken into account.

In a secondary analysis, the total incidence (not restricted to fallers) of hip fracture in the intervention boroughs will be compared with the incidence of hip fracture in the control boroughs, and a similar comparison will be made before the intervention started. Adjustment for possible time trends will be considered.

Primary outcome variables

- Hip fracture
- Admittance to nursing home, long term
- Death (all-cause mortality)

Secondary outcome variables

Other fall injuries

In each analysis, participants with a hip fracture or living in a nursing home at baseline will be excluded.

Statistical power

According to statistics from NPR before the intervention started, around 22% of the home dwelling elderly treated for a fall injury came from the intervention boroughs of Nordstrand and Østensjø.

If 22% of the patients with falls are exposed to the fall prevention intervention and 607 of all fallers suffer a hip fracture during a follow-up of five years (2015-2019), it will enable us to detect a relative risk reduction of 24% (RR= 0.76) at the 0.05 significance level with a power of 80%.

Data management and analysis

The Cohort Data is stored at Services for Sensitive Data (TSD) at the University of Oslo.

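### The stated 80% power belongs to a simpler comparison than the planned main analysis: it ignores Østensjø's September 2016 start and carries no variance for the 2012-2013 baseline correction, whose estimator is not named

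*Combined protocol and SAP*

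**What the plan says.** The Statistical power section rests on one conditional statement: "If 22% of the patients with falls are exposed to the fall prevention intervention and 607 of all fallers suffer a hip fracture" over five years (2015-2019), then "it will enable us to detect a relative risk reduction of 24% (RR= 0.76) at the 0.05 significance level with a power of 80" per cent. The 22% is the share of both intervention boroughs together among home-dwelling elderly treated for a fall injury, from registry statistics before the intervention. The split between the boroughs is not given.

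Four other places define what will be analysed:

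- **Timeline:** "Start of intervention in Østensjø borough is set to September 1, 2016". Nordstrand starts on 1 January 2015.
- **Exposure categories and Main analysis:** the comparison is "In the main analysis (2015-2019), fallers from the two intervention boroughs, Nordstrand (from January 2015) and Østensjø (from September 2016"), against fallers from the 13 other boroughs.
- **Statistical Analysis Plan, opening sentence:** "The investigators will use a controlled before and after study design to evaluate this intervention".
- **Main analysis, on the earlier period:** "A similar analysis will be performed before the intervention started using data from 2012-2013". The plan adds that borough differences found there will be allowed for, but does not say how. The section on the cohort says only "The study will follow each cohort participants prospectively and analyze the data by Cox proportional hazards regression or similar".

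The power section mentions neither the later Østensjø start nor the 2012-2013 data, and no event count is given for 2012-2013.

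**The concern.** This sentence is the plan's only statement of what effect the study can detect. It describes two groups compared once, with the full 22% exposed from the first day of 2015 to the last day of 2019. The planned comparison starts one of its two exposed boroughs 20 months late, leaves that borough's earlier fallers without a category, and then corrects for an estimated baseline difference that has sampling error of its own.

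At stake is interpretation. A wide or null result for hip fracture would be read against 80% power for a 24% reduction, which has not been shown for the analysis that will be reported. The statement also covers hip fracture only; nursing home admission and death, the other two primary outcomes, have no power figure.

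**Working it through.** **Inputs.** From the plan: two-group exposed share 0.22, 607 events, RR 0.76, level 0.05, power 80%, and the two start dates. Not in the plan, so assumed: Østensjø's share *s* of the 22% (30-70%), the timing of events within 2015-2019, and the number of events in 2012-2013.

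**1. The plan's own figure.** Schoenfeld's formula is D = (z₀.₉₇₅ + z₀.₈₀)² / [p(1−p)(ln RR)²].

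- (1.960 + 0.8416)² = 7.849; p(1−p) = 0.22 × 0.78 = 0.1716; (ln 0.76)² = 0.07532.
- D = 7.849 / (0.1716 × 0.07532) = 607.3.
- With 607 events, SE = 1/√(607 × 0.1716) = 0.0980, and power = Φ(0.2744/0.0980 − 1.960) = 0.7998.

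A one-sided test would give 87.6%, so the figure is a two-sided, single, after-only comparison.

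**2. Østensjø's start date.** January 2015 to August 2016 is 20 of 60 months. Let *f* be the fraction of Østensjø's 2015-2019 events that fall in those months: 20/60 = 1/3 at a constant event rate, or (1/3)² = 1/9 if fallers accumulate steadily from January 2015. With those events excluded, lost = 0.22·s·f, D = 607(1 − lost) and p₁ = (0.22 − lost)/(1 − lost).

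| s | f | D | p₁ | Power at 0.76 | RR detectable at 80% |
|---|---|---|---|---|---|
| 30% | 1/3 | 593.6 | 0.2025 | 76.6% | 0.751 |
| 50% | 1/3 | 584.7 | 0.1903 | 74.1% | 0.744 |
| 70% | 1/3 | 575.8 | 0.1778 | 71.2% | 0.737 |
| 30% | 1/9 | 602.5 | 0.2142 | 78.9% | 0.757 |
| 70% | 1/9 | 596.6 | 0.2064 | 77.4% | 0.753 |

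Counting the pre-start time as control instead gives 72-79%. I assume that the 607 includes Østensjø's pre-start events; the plan does not say. If it leaves them out, 22% is still too high an exposed share.

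**3. Baseline correction, illustration only.** Suppose the correction is a ratio of hazard ratios (2015-2019 over 2012-2013). Then Var = 1/(607 × 0.1716) + 1/(D_before × 0.1716). For D_before = 243 this is 0.00960 + 0.02398 = 0.03358, so SE = 0.183 and power = Φ(0.2744/0.183 − 1.960) = 0.322.

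| D_before (assumed) | Basis | SE | Power at 0.76 | Ratio detectable at 80% |
|---|---|---|---|---|
| 97 | 607 × (2/5)², fallers accumulating | 0.264 | 18% | 0.48 |
| 243 | 607 × 2/5, constant rate | 0.183 | 32% | 0.60 |
| 364 | 607 × 3/5, higher early rate | 0.160 | 40% | 0.64 |
| 607 | as many events in two years as in the later five | 0.139 | 51% | 0.68 |

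**4. Both features together.** With 243 baseline events, power goes from 32.2% to 30.5-32.0% over the range of *s* and *f* in step 2. For 97-364 events the extra loss from Østensjø's start is about 0-3 points. A Poisson simulation (200,000 runs, the 22% split equally, constant rate) gave 29.8% for 243 and 35.5% for 364, slightly below the formula's 31.0% and 38.5%.

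**5. Another possible estimator.** One staggered model with borough-group and period effects would use Østensjø's pre-start time as unexposed. At an assumed 607/5 = 121.4 events per year, it gives 42-43% power with a 2012-2014 baseline and 35-38% with 2012-2013 only. Covariate adjustment and side-by-side reporting were not computed.

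**The case against.** The best defence is that the power sentence is explicitly conditional, its arithmetic is correct, and it addresses the 2015-2019 main comparison, with 2012-2013 introduced as a separate, similar analysis. Powering the main contrast alone is defensible. This does not rescue the figure, because that contrast itself starts Østensjø in September 2016.

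The size of that first gap can fairly be called small. Cohort members become fallers only on a new fall injury, so fallers accumulate; if they do so from January 2015, the loss is 1-3 points, and the 9-point end needs a 70% Østensjø share and a constant rate. Choice of formula matters about as much: taking the variance from the expected split of events (107 and 500) gives 73.2% for the unmodified calculation. That stands as a comment on size, not on direction.

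It is also true that the cohort is a fixed registry population, the study period closed in 2019, and confidence intervals will show the precision achieved. No sample size decision hangs on this.

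A reader might infer that the study really has only 20-40% power. The documents do not support that. Those values hold for a before-after contrast that the plan does not name, with a 2012-2013 event count that it does not give. Allowing for baseline differences could equally mean covariate adjustment or side-by-side reporting, which would lose less. Nor is the cost of Østensjø's late start the same under every estimator: it is 1-9 points after-only, but under 2 points in a before-after contrast with 243 baseline events.

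**Conclusion.** The concern stands in limited form. The 80% is correct for a comparison that the plan does not make. For the after-only 2015-2019 comparison on the plan's own dates, power at RR 0.76 is about 71-79% and the detectable RR about 0.74-0.76, assuming that Østensjø supplies 30-70% of the 22%; the upper end applies if fallers accumulate from 2015.

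The absence of any variance for the baseline correction is certain; its size is not. If a ratio of hazard ratios is used, power is about 32% with 243 baseline events, 18-40% for 97-364, and 51% even with 607. These figures are illustrations, not estimates of the study's power. The consequence is a misleading planning statement that should be corrected; it does not invalidate the study.

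**What to change.** 1. Restate the power with an exposed share p₁ that counts Østensjø only from September 2016, using the actual borough split.
2. State whether Østensjø's fallers from January 2015 to August 2016 are excluded or assigned to a category.
3. Name the estimator that will allow for 2012-2013 borough differences. If it is a before-after contrast, recompute power with Var = 1/[D_after·p₁(1−p₁)] + 1/[D_before·p₀(1−p₀)], where p₀ is the intervention boroughs' share in 2012-2013 and D_before is the actual registry count. Note that this treats the two periods as independent and ignores clustering by borough (2 against 13), so it may still be optimistic.
4. Otherwise, keep the after-only figure, corrected for Østensjø's start, and label it as applying to hip fracture only and without correction for pre-existing borough differences.

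The cost is SAP wording and one recalculation from registry counts; the plan says data are available from 2010. Recruitment, follow-up and data items are unchanged. The downside is a less favourable stated detectable effect.

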Study Protocol and Statistical Analysis Plan

Does the Improved Coordination of Care for Fall- and Fracture Prevention in Oslo Have Effect on the Rate of Hip Fractures, Need of Nursing Homes or Death?

RCN296587

January 2. 2023

The study is an evaluation of a new patient follow-up for fall- and fracture prevention in the municipality of Oslo with improvement of coordination of care for elderly (65 years or older, 65+) at risk of fall injuries.

The two major innovations in this initiative are 1) the systematic approach to improving care coordination within the health care system as well as 2) including osteoporosis evaluation in the fall risk assessment in order to reduce risk of fall related fractures.

In this study, the two city boroughs of Nordstrand and Østensjø, who initiated the intervention, are compared with a control group consisting of the other 13 city boroughs of Oslo in a controlled before and after study design.

The care coordination implemented is in line of the framework Øvretveit used in his summary review "Does clinical coordination improve quality and save money?" (2011)ⁱ, and which WHO later adopted in their practice brief "Continuity and coordination of care" (2018)ⁱⁱ. The major steps in the intervention in Oslo are as follows:

- Needs assessment and user involvement. The intervention started with the chief medical officers in the areas of intervention realizing the health burden of hip fractures within their boroughs, as well as the lack of care coordination in the delivery of preventive measures. The steps of the intervention were developed as a cooperative effort with the local health professionals who delivered the services, the chief medical officers in the boroughs and specialists in geriatrics, osteoporosis and injuries at Oslo University Hospital.

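### The stated 80% power fits a simple 2015-2019 comparison with both boroughs exposed throughout; it does not describe the declared controlled before-after design, whose contrast and borough-level variation are left undefined

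*Combined protocol and SAP*

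**What the plan says.** The section Statistical Analysis Plan declares the design: "The investigators will use a controlled before and after study design to evaluate this intervention". The introduction names the groups: two boroughs "who initiated the intervention, are compared with a control group consisting of the other 13 city boroughs of Oslo".

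Under Main analysis, fallers in the intervention and control boroughs are compared over 2015-2019, with Nordstrand exposed from January 2015 and Østensjø only from September 2016. The paragraph then adds: "A similar analysis will be performed before the intervention started using data from 2012-2013". It ends: "Any differences between the intervention and control boroughs before the intervention started will be taken into account". No interaction term, ratio of hazard ratios or test is named for this.

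The model appears under The cohort: "The study will follow each cohort participants prospectively and analyze the data by Cox proportional hazards regression or similar". No borough random effect, frailty, robust variance or borough-level test is mentioned.

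Under Statistical power the inputs are: "If 22% of the patients with falls are exposed to the fall prevention intervention and 607 of all fallers suffer a hip fracture" over the five years 2015-2019. From these the plan claims to "detect a relative risk reduction of 24% (RR= 0.76) at the 0.05 significance level with a power of 80"%. No event count is given for 2012-2013.

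**The concern.** The power paragraph uses one period and one event count. A before-after contrast has two sources of sampling error, one from each period, and the earlier period is shorter. If the earlier contrast is subtracted, its variance adds, and the stated power is for a different quantity from the one the design is meant to deliver. A null result could then be given more weight against a 24% reduction than the data support.

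Two further features point the same way. The 22% treats both boroughs as exposed for all five years, although the plan's own dates leave the second unexposed for the first 20 months. And exposure is assigned by borough, while the model and the power calculation treat fallers as independent. Correcting for prior differences removes stable differences between boroughs, but not change over time that differs from one borough to another. If such change exists, model-based intervals are too narrow.

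**Working it through.** **Inputs from the plan.** After-period events 607; exposed share 0.22; RR 0.76, so |ln RR| = 0.2744; significance level 0.05, taken as two-sided because that reproduces the plan's figure; 2 intervention and 13 control boroughs. **Not in the plan:** the before-period event count n0, the relative size of the two boroughs, and the between-borough SD of change.

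**1. The plan's figure.** Variance of the log hazard ratio = 1/(607 × 0.22 × 0.78) = 1/104.16 = 0.00960, so SE = 0.0980. Power = Φ(0.2744/0.0980 − 1.96) = Φ(0.841) = 79.98%. The 80% is correct for this comparison.

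**2. Subtracting the 2012-2013 contrast.** Variance = 0.00960 + 1/(n0 × 0.22 × 0.78), and power = Φ(0.2744/SE − 1.96). The RR detectable with 80% power is exp(−2.80 × SE), where 2.80 = 1.96 + 0.84. The assumed counts are:

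- 97 = 607 × (2/5)², if faller time builds up from zero in each period. The rule "The individuals in the cohort are all registered as non-fallers until they are registered with a new fall injury" points this way.
- 243 = 607 × 2/5, if the yearly number of events is constant.
- 607, as many events as in the after period, and 1,214, twice as many, as generous cases.

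| n0 (assumed) | SE | Power at RR 0.76 | RR detectable at 80% |
|---|---|---|---|
| 97 | 0.264 | 18% | 0.48 |
| 243 | 0.183 | 32% | 0.60 |
| 607 | 0.139 | 51% | 0.68 |
| 1,214 | 0.120 | 63% | 0.71 |

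The added term is positive for any finite n0, so power always lies below the 79.98% of step 1.

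**3. The second borough's start date, without subtraction.** Assume each intervention borough supplies 11 of the 22 percentage points. Østensjø is exposed for 40 of 60 months: 11 × 40/60 = 7.33 points, so 18.33 points are exposed in all. Leaving out its unexposed time, events = 607 × (18.33 + 78)/100 = 584.7 and the exposed share = 18.33/96.33 = 0.190. Power = Φ(0.2744 × √(584.7 × 0.190 × 0.810) − 1.96) = 74%. Combined with subtraction at n0 = 243, it is 31%.

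**4. Cross-check with an intervention-in-force model.** This was simulated with Poisson counts, borough and period effects, and the late borough's earlier time counted as unexposed. It assumed two boroughs with 11% of fallers each, thirteen with 6% each, and no borough-specific change. Power at RR 0.76 was 34% with 243 before-period events, and between 22% and 45% for 97 to 607. This model does not restore 80% either.

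**5. Borough-specific change.** Let each borough's log rate change by its own amount, with standard deviation SD. The true variance of the before-after contrast then gains SD² × (1/2 + 1/13) = 0.577 × SD². A test that ignores this has type I error 2 × [1 − Φ(1.96/√(1 + 0.577 × SD²/v))]. With v = 0.0336 (n0 = 243), this is 5.5%, 7.0% and 13.1% at SD 5%, 10% and 20%. The simulated in-force model gave 5.1%, 6.4% and 10.0%.

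**The case against.** The power paragraph matches what the plan labels its main analysis: same period, same population. How prior differences will be handled is not written. Covariate adjustment, or using 2012-2013 only as a check of comparability, would also fit the words and cost less variance. That stands: reading the phrase as a full difference of log hazard ratios is natural for the declared design, but it is an interpretation. It does not rescue the 80%. If the earlier period is only inspected, prior borough differences are not removed, and step 3 still gives about 74% under its equal-size assumption.

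A reader might infer that the study has 32% power and would miss a true 24% reduction about two times in three. The documents do not support so definite a statement: 243 is one assumed count within a range, and the subtraction is not specified. Nor is the 80% an arithmetic slip; it reproduces.

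A reader might also infer that the planned p-values are invalid because of clustering. The documents give no borough SD. At an SD of 5% or less, with the stated event count, the inflation is negligible. The words allowing a model similar to Cox do not rule out a borough-level term, so this is an omission and not a wrong choice.

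Finally, follow-up ended in December 2019 and the plan is dated January 2023, so power sets no sample size and a null result can be judged by its confidence interval. That is fair and limits the consequence. What remains is that the contrast must be defined before that interval can be read, and that the published power should describe it.

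**Conclusion.** The point holds in this form and should be fixed. The 80% applies only to a 2015-2019 comparison of independent fallers with both boroughs exposed throughout. For a contrast that subtracts 2012-2013, power is below 80% whatever the before-period count: about 18% to 51% for assumed counts of 97 to 607, with a detectable RR of about 0.48 to 0.68 in place of 0.76. The direction is certain once the earlier contrast is subtracted; the size rests on the assumed count. The 74% for the simple comparison rests on assuming equal-sized boroughs. All these figures concern hip fracture; the plan gives no power for nursing home admission or death.

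The missing borough-level variance is a real gap of unknown size. It warrants a sensitivity analysis and does not on its own discredit the planned inference.

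**What to change.** 1. **Define the before-after estimand.** One option is a model with borough terms, calendar-period terms and an indicator for the intervention being in force. The indicator follows the plan's own start dates, so Østensjø's time before September 2016 counts as unexposed.
2. **Restate power, or the detectable RR, for that contrast.** The total before-period event count can be taken from data already held, without relating the intervention to outcomes. No enrolment is added.
3. **Report one borough-level sensitivity analysis beside the model-based interval.** Examples are placebo reassignment of the two start dates across boroughs (15 × 14 = 210 ordered assignments, smallest p = 1/210 = 0.0048) or a random borough-by-period effect. Either would do.
4. **State the limits.** Inflation from ignoring borough-specific change depends on an unknown SD; the conditional figures in step 5 of the working can be given. Placebo reassignment assumes exchangeable boroughs and does not correct for the two boroughs having initiated the intervention themselves.

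The cost is SAP wording and a little more analysis: 210 refits per outcome if placebo reassignment is chosen. The downside is a less favourable stated power and somewhat wider intervals. In simulation with 243 before-period events and no borough variation, ranking studentised estimates over the 210 assignments had 30% power at RR 0.76, against 34% for the model-based in-force test.
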